A technology-based approach using computers and mobile devices (smart phones and tablets) promises to meet this necessity with high flexibility and accessibility, and minimizes the cost of the intervention in busy health care settings. Also, a technology-based intervention that does not involve face-to-face interactions could work better for many women from cultures where breast cancer is still a stigmatizing experience. Bespite the high potential, few technology-based interventions are available for ethnic minority breast cancer survivors, especially for Asian Americans. Therefore, based on Preliminary Studies (PSs), the research team has developed and pilot-tested a theory-driven technology-based information and coaching/support program that: (a) is tailored to Asian American breast cancer survivors by incorporating actual data on individual sub-ethnic groups cultural attitudes from PSs; (b) uses multiple languages; (c) provides both group and individual (real-time and personalized) coaching/support by culturally matched bilingual health care providers; (d) incorporates peer support through a social media function; and (e) integrates existing general and culture-specific evidence-based educational content from scientific authorities. Among over 71 sub-ethnic

groups of Asian Americans,⁴⁶ only three sub-ethnic groups (Chinese, Korean, and Japanese) were selected for the program development for the convenience of the approach (e.g., language). Within Asian Americans, Chinese are the largest sub-ethnic group,^{47,48} Koreans are the fastest growing sub-ethnic group,^{47,48} and Japanese are the sub-ethnic group at the highest risk of breast cancer.^{1,2,11,49}

Goals/Aims

The purpose of the proposed randomized intervention study is to test the efficacy of the technology-based information and coaching/support program for Asian American breast cancer survivors (TICAA) in enhancing the women's breast cancer survivorship experience.

The **specific aims** of the study are to:

Aim 1. Determine whether the intervention group (who uses the TICAA and the information on breast cancer by the American Cancer Society [ACS]) will show significantly greater improvements than the control group (who uses only the information on breast cancer by the ACS) in **primary outcomes** of the TICAA (needs for help, physical and psychological symptoms, and quality of life) from baseline (pre-test) to Time Points 1 (post 1-month; primary) and 2 (post 3-months; secondary).

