The data are mainly collected through the Internet survey questionnaire. When potential participants visit the project Web site (after receiving/reviewing a study announcement), they will be asked to review the informed consent. When participants click I agree to participate, they will have given their consent. Then, after checking them against the inclusion criteria and quota requirements, only those who meet the criteria and requirements will be automatically assigned a serial number, and randomized into two groups using an automated random number generator accessible through the Web site.

Then, the women will be asked to fill out the Internet survey questionnaire (if requested, paper-and-pencil questionnaires will be provided/used, or research staff will assist in administering the Internet surveys over the phone.) and sign up the Web site by creating their own ID and passwords. Whenever they visit the Web site, they need to use the ID and passwords to log in the site. If they want, they can change their ID and passwords. Then, both groups will be provided with an electronic instruction sheet on when they need to come back and fill out additional questionnaires and/or use the program.

Biweekly, the research team will send reminders and thank-you emails. Two weeks before the end of the 1st month, both groups will be asked to fill out the next set of the instruments by the end of the 1st month. Then, 2 weeks before the end of the 3rd month, both groups will be asked to fill out the next set of the instruments by the end of the 3rd month.

O Description of research instruments to be used (e.g., questionnaires, surveys, interview or focus group guides, scales)

Multiple instruments will be used: the Support Care Needs Survey-34 Short Form (SCNS-34SF),⁵⁰ the Memorial Symptom Assessment Scale-Short Form (MSAS-SF),⁵¹ the Functional Assessment of Cancer Therapy Scale-Breast Cancer (FACT-B),⁵² the modified Questions on Attitudes, Self-Efficacy, Perceived Barriers, and Social Influences (QASPS),⁵³ the Cancer Behavior Inventory (CBI),^{54,55,56} the Perceived Isolation Scale (PIS),^{57,58} the Personal Resource Questionnaire (PRQ-2000),⁵⁹ and 27 questions on background characteristics, level of acculturation, and disease factors. The reliability and validity of all the instruments have been established among Asian Americans. Cronbach's alpha of individual instrument ranged from .76 to .96 among Asian Americans.

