Aim #1: Effects on Primary Outcomes. Separate intent-to-treat general linear models 86 will be used to examine differences in continuous outcome measures by intervention group at each time point, adjusting for baseline outcome and any variables that demonstrate imbalances in preliminary analyses. Model assumptions will be assessed, and modifications will be implemented as necessary to improve mode fit. Differences in continuous outcome measures over time will be examined using an intent-to-treat linear mixed-model growth curve analysis with SAS Proc Mixed.86 Mixed models will be used in which all available data collected during follow-up is used.87,88 Separate mixed effects regression models will be generated for each outcome measure. Both random slopes and intercepts will be modeled to represent the subject level deviation from the average, or fixed-effect, slope over time and intercept, respectively. Restricted maximum likelihood estimation will be used, and the most appropriate covariance structure will be examined. The outcomes will be analyzed as repeated observations of the dependent variables, with mean-centered baseline outcome scores serving as a covariate. Other predictors will include intervention group, time from baseline to follow-up, the interaction of group and time, and the interaction of baseline measures and time. Baseline outcome and group will be analyzed as time-independent covariates. Other demographic or treatment timeindependent variables identified in preliminary analyses may be included as covariates. Main effects and higher order interaction terms will be examined. The Akaike information criterion will evaluate overall model fit and to select the best-fitting longitudinal change pattern.89

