Aim #2: Mediation of Intervention effects. Sequential process random regression growth curve modeling90 will be performed to explore the hypotheses that attitudes, self-efficacy, perceived barriers, and social influences, separately, mediate the relationship between intervention group and change over time in primary outcomes. Specifically, we will examine whether the women who receive the TICAA show more favorable changes on the mediators at post-intervention and the follow-up periods relative to pre-intervention than do those in the control group. Mediational analyses will be performed to examine whether there is statistical support for the view that the putative mediator variables actually mediate effects of the TICAA on participants' needs for

help, physical and psychological symptoms, and quality of life. Although various methods are appropriate for evaluating mediation in this setting, random regression growth curve modeling90 was chosen as it prospectively and longitudinally tests the three criteria of mediation proposed by Baron and Kenny. 91 Modeling will rely on incorporating time varying [mediator] as a predictor of outcome in each sequential assessment. To test the mediation hypothesis, individual slope and intercept parameters will be estimated for each participant based on intervention, mediator, and outcome. The intercept parameters will be coded to represent the value of the linear growth trajectory for each participant at baseline. The sequential process, or lagged approach, will allow for stronger inference regarding causality. Model assumptions will be assessed, and transformations will be applied as necessary. A series of four regressions will be used to test each of the mediational chains according to the criteria specified by Baron and Kenny.91 Significant decreases in outcome will be assessed using the Sobel test. 92

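### The baseline that both Aim 1 models adjust for is collected after randomisation with no stated time of arm disclosure, and the other Aim 1 covariates are not fixed in advance

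*Combined protocol and SAP*

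**What the plan says.** **Order of events.** In the combined protocol and SAP, under *Describe the procedures for data collection*, a woman consents on the website, is checked against the inclusion criteria and quotas, and is then "randomized into two groups using an automated random number generator accessible through the Web site". The next step reads "Then, the women will be asked to fill out the Internet survey questionnaire". On request a paper form is used, or "research staff will assist in administering the Internet surveys over the phone". She then creates a log-in, and after that both groups receive an electronic instruction sheet. No outcome survey before randomisation is described, so this one is the baseline.

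**Intended meaning of baseline.** *Goals/Aims* measures improvement "from baseline (pre-test) to Time Points 1 (post 1-month; primary) and 2 (post 3-months; secondary". The *Aim #2* analysis asks whether the mediators of women given the TICAA change more favourably "relative to pre-intervention than do those in the control group". Baseline is therefore meant to precede the intervention. *Components* starts individual coaching on enrolment and does not tie that start to a submitted survey.

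**Models.** Under *Aim #1: Effects on Primary Outcomes*, the general linear models are fitted "adjusting for baseline outcome and any variables that demonstrate imbalances in preliminary analyses". The mixed models analyse the repeated follow-up scores "with mean-centered baseline outcome scores serving as a covariate", and further "variables identified in preliminary analyses may be included as covariates".

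**Known design factors.** The intervention section plans 55 women from each of three sub-ethnic groups in each arm. *Population to be studied* splits enrolment into 210 women at Duke, who have finished, and 120 still to be recruited at Emory. Neither factor is named as an Aim 1 covariate.

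**The concern.** Baseline adjustment is safe when the covariate cannot depend on the arm. Here the covariate is a set of self-reported scores taken after assignment. If a woman, or a staff member reading her the questions by phone, already knows the arm, the answers can differ by arm for that reason alone. Adjusting for them then moves the estimated effect, in a direction that depends on how the answers shift. The order also allows a woman to be randomised and never supply the covariate, whether or not she knows her arm.

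The second issue is separate. A covariate list settled by observed imbalance, with no test or threshold given, or left optional, means that the models for eight primary outcome measures are not determined before the data are seen. The imbalance rule need not use outcomes. The optional clause is where most of the freedom lies. The rule also looks in the wrong place: if 55 per arm is achieved in each sub-ethnic group, that factor shows no imbalance among the women randomised and would never be selected, although the design is built around it.

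**Working it through.** **1. The plan's own sample size (*Recruitment*).** Inputs: eight measures, two-sided test, 0.5 SD, 80% power, 35% attrition.
- Type I error: 0.05/8 = 0.00625, critical z = 2.734.
- Normal approximation: 103 per group. Noncentral t, with relative efficiency 1 for a uniform distribution: 105 per group (power 80.4%), as stated.
- Attrition: 105/0.65 = 161.5, so 162 per group and 324 in total, against 330 planned.

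The sample size reproduces, and the present point does not depend on it.

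**2. Is the arm known at baseline?** The stated order is consent, eligibility and quota check, randomisation, survey, log-in, instruction sheet. The sheet is the only arm-relevant message in that section and it follows the survey. It is not said to be the first notice of the arm. Masking of phone staff is not stated, and the start of coaching is tied to enrolment, not to the survey. The text therefore suggests disclosure after baseline without establishing it.

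**3. What a shift would do.** The shift d and the baseline–follow-up correlation r are assumptions; the documents give neither. Let knowledge of the arm move the difference in mean baseline by d (unit SDs).
- Arm concealed until the survey is submitted: d = 0, bias = 0.
- Shift not carried to follow-up: bias has size r × d. For d = 0.05 this is 0.5 × 0.05 = 0.025 to 0.7 × 0.05 = 0.035 SD. For d = 0.10 it is 0.05 to 0.07 SD. Divided by 0.5 SD, the range is 5–14% of the planned effect.
- Same shift persisting at follow-up: bias has size (1 − r) × d with the opposite sign, from 0.3 × 0.05 = 0.015 to 0.5 × 0.10 = 0.05 SD. At a given d and r in this range, that is equal (r = 0.5) or smaller (r > 0.5).

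**4. Consequence in the non-persisting case.** Take 107 per arm (165 × 0.65 = 107.25; the 35% applies by Time Point 2, so this is cautious for Time Point 1). SE = √((1 − r²) × 2/107) = 0.1184 at r = 0.5 and 0.0976 at r = 0.7. Type I error = P(Z > 2.734 − bias/SE) + P(Z < −2.734 − bias/SE).

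| d | r = 0.5 | r = 0.7 |
|---|---|---|
| 0.05 | 0.0074 | 0.0097 |
| 0.10 | 0.0112 | 0.0221 |

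The nominal level is 0.00625. If a 0.10 shift works against the TICAA instead, power at 0.5 SD falls from 93.2% to 85.7% (r = 0.5) or from 99.2% to 95.3% (r = 0.7).

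**5. Cost of omitting sub-ethnic group under enforced balance.** Assume it explains R = 5–15% of variance in baseline and follow-up alike, with within-group correlation r = 0.5–0.7. Overall correlation t = R + (1 − R)r. Partial R² = 1 − (1 − R)(1 − r²)/(1 − t²). Interval widening = 1/√(1 − partial R²) − 1.
- R = 0.05, r = 0.7: t = 0.715, partial R² = 0.9%, widening 0.4%.
- R = 0.15, r = 0.5: t = 0.575, partial R² = 4.8%, widening 2.5%.

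**6. Cost of adding the terms.** Two degrees of freedom for three sub-ethnic groups and one for institution. With 214 women (330 × 0.65 = 214.5), residual degrees of freedom go from 211 to 208, and √(211/208) − 1 = 0.7% on the standard error if the terms explain nothing.

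**7. Reach.** Reordering can still apply to 120/330 = 36% of the women. The covariate list can be fixed for all 330.

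**The case against.** The strongest reply is that the sequence, read naturally, already protects the baseline. The instruction sheet comes after the survey and log-in, and if that is when women learn their arm, the bias is zero and only one clarifying sentence is missing. That reading is plausible, and it is why no bias can be asserted. It is not stated, so it cannot be relied on either.

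The bias sizes are also assumed. They shift a whole arm, whereas phone help is by request and could touch only some women, and a persisting shift reverses the sign. All of this stands. The figures show scale only, and even the lowest power shown, 85.7%, is above the planned 80%.

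On missing baselines, *Preliminary Analysis & Missing Data* plans to examine the missingness mechanism and impute. This helps, but it does not address a randomised woman without a baseline specifically, and it does not prevent the gap.

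On covariates, baseline outcome is prespecified in both models, and leaving out a balanced factor costs little precision and does not bias the effect. That is right. What remains is that the rest of the model is open. Aim 3 may examine background factors as moderators, but it is exploratory and does not fix the Aim 1 covariates.

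A reader might infer two stronger things. One is that coaching reaches women before baseline; the pre-test and pre-intervention labels show that this is not intended. The other is that allocation is unrestricted, so that 55 per cell is implausible; the method is not described, and a quota check precedes randomisation. How 55 per cell is reached is a reporting detail.

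**Conclusion.** The point holds as an unprotected sequence and an unfixed model, not as a demonstrated bias.

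- **Sequence.** The covariate used in both Aim 1 models is collected after assignment, and no text says when the arm is disclosed. Bias is zero under concealment until submission and of unknown size and direction otherwise. The 0.025–0.07 SD illustration rests on an assumed shift of 0.05–0.10 SD across the whole arm, no persistence to follow-up, and an assumed correlation of 0.5–0.7. A reader might take those figures as the trial's bias, but no document supplies the inputs.
- **Covariates.** Choice by observed imbalance, or at discretion, should give way to a fixed list. The precision gain is small (0.4–2.5% in interval width, on assumed variance shares of 5–15%). The main gain is a model settled in advance. Nothing here shows that power or sample size is inadequate.

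The change is worth making because it is cheap. Confidence is moderate, since one unreported fact, the time of disclosure, decides whether the first part matters.

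**What to change.** (a) Before any outcome comparison by arm, replace the imbalance-selected and optional covariates in every Aim 1 model, for all 330 women, with a prespecified set: baseline outcome, sub-ethnic group (three levels) and enrolling institution or period (Duke or Emory).

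(b) For the remaining 120 women, have the website randomise only after the baseline survey is submitted. This also removes the masking question for phone help at baseline and the problem of randomised women with no baseline. For the 210 Duke women, report the order actually used and when the arm was disclosed.

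Cost: three model degrees of freedom (standard error about 0.7% larger if the terms explain nothing) and a reordered web step. The sample size does not change. The downside is two enrolment sequences in one trial, and the Duke order cannot be altered, so for those women the question can be answered only by reporting.

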A total of 330 Asian American breast cancer survivors will be recruited. Because information is limited on which to base power analyses, estimates are based on a two-sided Mann-Whitney test (assuming a uniform distribution) using an estimated effect size equal to 1/2 of a standard deviation, as suggested in the literature. In addition to being clinically meaningful, large effect sizes demonstrated in PS4 suggest that 0.5*SD is a statistically meaningful effect size to assume. Sample size is based on 80% power, and a type I error rate equal to 0.00625 to account for eight primary outcome measures modeled within the two primary aims (group main effects). Accordingly, group sample sizes of 105 each achieve 80% power to detect a difference of 0.5*SD between group means overall in a single follow-up period. The primary analysis will be an assessment of differences by intervention group in changes from baseline to Time Point 1, or one month post intervention. A secondary analysis will include similar modeling for sustainability of

intervention effects, or for changes from baseline to Time Point 2. Assuming an attrition rate of 35% by the Time Point 2, 330 Asian American breast cancer survivors would be an adequate number for the study with multiple outcomes. Considering the attrition rates reported in the literature^{66–68} and in PSs, the assumption of a 35% attrition rate is reasonable.

At the completion of their participation, the participants will be reimbursed with \$50 electronic gift cards for their participation. The reimbursement will be prorated. The participants will be allowed to choose "do not want to respond", which will NOT be considered missing data. The amount was determined based on preliminary studies.

o Description of recruitment materials and their use

Sample study announcement, sample study announcement in flyer format, and flyer for TICAA recruitment will be distributed through and displayed on cancer support groups and communities/groups for Asian Americans.

o Describe the procedures for data collection

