O Describe any other study-related interactions or interventions: **The Intervention: The**TICAA

This study consists of two groups of research participants: (a) 165 Asian American breast cancer survivors (55 per sub-ethnic group) who do not use the TICAA, but use the information on breast cancer by the American Cancer Society (ACS)(a control group); (b) 165 Asian American breast cancer survivors (55 per sub-ethnic group) who use the TICAA and the information by the ACS (an intervention group). The ACS website includes information on treatment, prevention, genetics, causes, screening, testing, coping, clinical trials, research findings, and statistics related to breast cancer in multiple languages including Mandarin Chinese and Korean. At the completion of the study, both will be allowed to use or continue to use the TICAA.

Theoretical Bases, Information Architecture, and Menus. The TICAA was developed based on the findings from PSs using the information mapping approach.⁶⁹ The TICAA is theoretically based on the Bandura's theory. Based on the Bandura's theory, ^{70–72} most self-management programs include coaching/support and information interventions as part of the program content.⁷³ Likewise, the TICAA includes group and individual (real-time and personalized) coaching/support by health care providers, peer coaching/support, and information to change the women's attitudes, self-efficacy, perceived barriers, and social influences. The TICAA uses a free-form matrix information architecture⁷⁴ and includes menus based on the three components (see below). Graphic User Interface controls⁷⁵ (e.g., push buttons, check boxes, drop-down lists) are used. Presentation styles (e.g., colors, menus, etc.) are tailored based on PSs.

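### The plan states 55 women per sub-ethnic group in each arm but describes no stratified or blocked allocation that would produce those cells

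*Combined protocol and SAP*

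**What the plan says.** The section on the TICAA intervention sets out two arms of identical composition: "165 Asian American breast cancer survivors (55 per sub-ethnic group) who do not use the TICAA" and "165 Asian American breast cancer survivors (55 per sub-ethnic group) who use the TICAA and the information by the ACS". The introduction names the groups: "only three sub-ethnic groups (Chinese, Korean, and Japanese) were selected for the program development". This makes six cells of 55, matching the total under Recruitment: "A total of 330 Asian American breast cancer survivors will be recruited".

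Allocation is described once, under the procedures for data collection. After online consent, women are admitted "after checking them against the inclusion criteria and quota requirements", given a serial number, and "randomized into two groups using an automated random number generator accessible through the Web site". The quotas are not defined. No stratification factor, block size, stored list or rule for a full cell is described.

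Under Population to be studied, 210 of the 330 have already been recruited and have finished at the first university, and 120 are to be recruited at the second. The split of the 210 by arm and sub-ethnic group is not reported.

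The Aim 1 analysis adjusts for the baseline outcome and for whichever variables turn out to be imbalanced. It names neither sub-ethnic group nor recruitment phase.

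**The concern.** Equal cells in every arm-by-group combination normally come from restricted randomization, and none is described. The quota check does not fill the gap. It comes before the arm is known, so it can hold a sub-ethnic group to 110 women but cannot by itself divide them 55/55.

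Sub-ethnic group matters here because it determines the social media site, the matched interventionist and part of the educational content that a woman in the TICAA arm receives. Uneven arms within a group cost some balance and precision on a factor built into the intervention. If equality were instead enforced by closing a full arm, later assignments in that group would be known in advance. In either case, choosing adjustment variables by observed imbalance leaves the primary model open until the data are seen.

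**Working it through.** **Inputs.** Total 330; 165 per arm; 55 per sub-ethnic group per arm; three groups (Introduction, Recruitment, TICAA section). Effect 0.5 SD, two-sided alpha 0.00625, power 80%, attrition 35% (Recruitment). Already recruited 210, remaining 120 (Population to be studied).

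**1. The plan's own figures reproduce.**
- Cells: 6 × 55 = 330, so 110 women per sub-ethnic group over both arms.
- Alpha: 0.05/8 = 0.00625, as in "a type I error rate equal to 0.00625 to account for eight primary outcome measures".
- Arm size: 2(z₀.₉₉₆₈₇₅ + z₀.₈₀)²/0.5² = 2(2.734 + 0.842)²/0.25, which rounds up to 103. The exact two-sided t-test gives 104.2, hence 105, with power 0.804. This agrees with "group sample sizes of 105 each achieve 80% power" if the Mann-Whitney test is taken as being as efficient as the t-test.
- Attrition: 330 × 0.65 = 214.5, which covers 2 × 105 = 210.

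**2. If allocation is simple 1:1.** The number assigned to TICAA among 110 women is Binomial(110, 0.5).
- P(exactly 55) = C(110,55)/2¹¹⁰ = 0.0759.
- P(exactly 55 in all three groups) = 0.0759³ = 0.00044, about 1 in 2,290.
- SD = √110/2 = 5.2. The central 95% range is 45 to 65 for a cell and, with 330 women, 147 to 183 for an arm.

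**3. If an arm were closed at 55 within a group.** The women left when the first arm fills all go to the other arm.
- Expected number per group = 110 × C(110,55)/2¹¹⁰ = 110 × 0.0759 = 8.35. Simulation gives a mean of 8.3, with 5th to 95th percentile 1 to 19.
- Over three groups the mean is about 25 (10 to 42), and 25/330 = 7.6%.

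**4. Effect on power.** With 65% retained in each arm, power = Φ(0.5/√(1/n₁ + 1/n₂) − 2.734).
- 165/165 enrolled (107.25 each analysed): 82.3%.
- 147/183 enrolled (95.55 and 118.95 analysed): 81.7%.

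**5. What blocking the last 120 can achieve.** Assume, for illustration only, that the 210 were 70 per group and were allocated simply.
- P(35/35 in one group) = C(70,35)/2⁷⁰ = 0.095. For all three it is 0.095³, about 0.09%.
- SD of the existing split = √70/2 = 4.2. If the next 40 divide 20/20, final cells still range over about 55 ± 8, that is 47 to 63.

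Blocking from now on prevents further drift but does not remove imbalance already present.

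**The case against.** Several counter-arguments have force.

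- **The text never calls the generator simple or unrestricted.** A random number generator can drive a stratified blocked list, which would give 55 per cell with no long forced run. This stands: the calculations above are conditional, and what is established is that the method is not stated.
- **The 55 may be a planning target and the quota a sub-ethnic total.** This is the natural reading of a check made before assignment. Nothing is then forced, and the consequence is cells of about 45 to 65. This also stands.
- **Exact cells are not needed.** Power is set for the overall two-arm comparison, and the loss is 82.3% − 81.7% = 0.6 percentage points. This stands as regards power.
- **Adjustment is already planned.** Only in part: the rule depends on which imbalances are observed and does not commit to sub-ethnic group.
- **Blocks are predictable too.** The expected determined run at the end of a block is 4/3 in a block of 4 and 3/2 in a block of 6, so (1.33 + 1.50)/10 = 28% of assignments are fixed by the earlier ones in their block. Those can be foreseen only by someone who knows the block size and position. A closed arm gives one unbroken run that anyone aware of the cap and the counts could foresee.

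A reader might go further and infer that the last allocations are forced and not random, that about a fifth of the second-phase allocations (25/120 = 21%) are affected, and that arm is therefore tied to recruitment phase. The documents do not support this. They state no cap by arm. The 21% needs a near-even split of the first 210, which is not reported. Even with a cap, the phase difference has no systematic direction. If 70 per group came first, the Duke-minus-Emory difference in the proportion assigned to TICAA has mean zero and SD (√210/2)(1/210 + 1/120) = 9.5 percentage points. Simple allocation gives √(0.25/210 + 0.25/120) = 5.7. That is extra chance variation, which a phase term handles. Nor do the documents describe a recruiter who sees running counts; assignment is automatic on the website.

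**Conclusion.** The point holds as a mismatch between a stated layout and the mechanism described for reaching it. Under simple 1:1 allocation the six cells of 55 would be met about once in 2,290 trials, with typical cells of 45 to 65. Under a cap by arm, about 8 assignments per group would be predetermined; this is a conditional figure, since no such cap is stated. How many of those would fall in the second recruitment phase cannot be worked out without the split of the 210.

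The effect on power is negligible. What is at stake is balance on a factor that shapes the intervention, unpredictability of assignment, and precision of the Aim 1 estimates. All figures assume 110 women per sub-ethnic group and a fair 1:1 draw. With 120 women still to be allocated, the change is worth making now.

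**What to change.** 1. Report how the 210 women were allocated and their split by arm and sub-ethnic group. This comes first, because it shows how much imbalance already exists.
2. Allocate the remaining 120 by permuted blocks of varying size, stratified by the three sub-ethnic groups, generated in advance and concealed within the website.
3. Define the quota as a sub-ethnic total only, never as a limit on an arm within a group.
4. Restate 55 per cell as a target, since blocking the last 120 cannot undo an earlier imbalance.
5. Prespecify sub-ethnic group and recruitment phase as fixed factors in the Aim 1 models, in place of adjusting only for variables that show imbalance. The model then also reflects the stratified allocation.

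The cost is one protocol paragraph, one tabulation of existing data, a stored allocation list in place of live draws, and three model degrees of freedom (two for sub-ethnic group, one for phase). No extra participants are needed. The small downside is some predictability within blocks, which concealment and varying sizes limit.
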